4.5 Sub-group analyses

Subgroup analyses will be performed within subgroups defined by the following baseline characteristics:

- Age class (<65 yrs, \geq 65 yrs),
- Gender,
- Race/ethnicity.

Within each subgroup level, analyses (descriptive summaries and ANOVA models) will be performed on the primary endpoints according to the methods defined for the primary analysis in Section 7.1.1.

In the ANOVA models, when presenting the analysis by subgroup, the covariate related to the subgroup will not be considered.

When performing MI for subgroups, the same MI as created for the main primary analysis will be used, by applying the related filter (i.e., subgroup analysis will not involve additional MI). If a specific level in subgroup analysis doesn't contain any missing, estimates of proc mixed will be considered (without using MI).

At the time of BDRM, categories of the subgroups above can be combined if the number of patients into categories is found to be too small or subgroups variables can be removed if categories are unbalanced.

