3.3 Sample size justification

The sample size of the study is calculated based on results from literature [5-8]. Evaluation of the efficacy for this study is being accomplished through estimation of a 95% confidence interval. No hypotheses are specified for this study and no p-values are being calculated but for descriptive purposes, therefore no level of significance is specified.

Considering a randomization ratio 1:1 (reparixin vs. placebo), a sample size of 60 evaluable subjects is considered adequate for assessing the difference between groups in primary endpoints, i.e., change from baseline in OI at day 7 and VFD at day 28.

The given sample size will provide a reasonable precision in the estimation of group differences in primary endpoints to an expected margin of error for a 95% one-sided confidence interval of at most 46.5% the standard deviation, whatever it is:

Standard/Forms/Template				
Title		Statistical Analysis Plan Template		
Code		Version	Effective Date	Page
PPD		01	29 Aug 2022	20 of 78

- Assuming a standard deviation of 11.5 points for OI, the 95% one-sided confidence interval for the difference between groups will have a width of 5.35 points;
- Assuming a standard deviation of 8 days for VFD, the 95% one-sided confidence interval for the difference between groups will have a width of 3.75 days.

If 10% of enrolled patients will not be evaluable for primary analysis, the total number of patients to be enrolled will be approximately 66.

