3.5.1 Primary endpoint

- Change in oxygenation index (OI) from baseline to day 7 [study day: date/time]
OI defined as: % mean airway pressure x FIO₂/PaO₂ (A difference between groups in 7-days OI of 6.6 points was significantly associated with 28-days mortality (Go et al., 2016). Thus, such a difference in the change in 7-days OI, ranked as the most important endpoint, will be valued as a proxy of clinical success)
- Ventilator free days (VFD) at day 28 [study day: date/time]

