For the imputation of Day 7 missing data, rules described in section 0 will be applied, and following the estimand definition, for missingness due to treatment discontinuation or any other reason (whichever the reason), MI-RD regression model will be created by including treatment, OI baseline value (imputed as described in this section), gender and age class (<65, >=65 years) as covariates (further details about the MI process are described below).

If there are not enough retrieved dropouts for convergence of MI-RD regression model, the Copy Reference approach will be used using OI baseline value, gender and age class (<65, >=65 years) as

Standard/Forms/Template				
Title		Statistical Analysis Plan Template		
Code		Version	Effective Date	Page
PPD		01	29 Aug 2022	43 of 78

covariates. Imputation of values in the two treatment arms will be done using the non-missing values from all the patients in the control group. The final decision on the use of the MI-RD vs Copy-Reference will be done at the time of the analysis and reported in the CSR.

Whether for MI-RD or Copy-Reference approach, the adjusted estimated changes from baseline for each treatment arm together with the corresponding 95% confidence intervals will be shown. The difference between Reparin and placebo in the change from baseline at Day 7 will be displayed together with the corresponding two-sided 90% confidence interval (in order to reflect the one-sided 95% confidence intervals). One-sided p-value (alpha=0.05 one-sided) will also be displayed for descriptive purpose.

MI process will be implemented as follows:

STEP1: Run MI for OI baseline missing data on 1000 imputations using:

CCI

Use numeric variable in the MCMC model.

At the blinded DRM, a discussion on the pattern of missingness will be held and it will be evaluated if data show a monotone pattern. If it will be evaluated that no monotone pattern is there, the statement “impute=monotone” will be deleted from the SAS code.

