1. Missing data at Day 28 will be imputed using the specified MI regression model. According to MI-RD approach, only non-missing values from retrieve dropouts will be used to inform the MI regression model. A total of 1000 datasets will be created. These datasets will be utilized in Step #2.
2. Each of the 1000 dataset with observed and imputed data will be analyzed using the ANOVA model. Rubin's rule will be used for combining results to draw inference.

If there are not enough retrieved dropouts for convergence of MI-RD regression model, the Copy Reference approach will be used using gender and age class (<65, >=65 years) as covariates. Imputation of values in the two treatment arms will be done using the non-missing values from all the patients in the control group. The final decision on the use of the MI-RD vs Copy-Reference will be done at the time of the analysis and reported in the CSR.

The difference between Reparixin and placebo at Day 28 will be displayed together with the corresponding two-sided 90% confidence interval (in order to reflect the one-sided 95% confidence intervals). One-sided p-value (alpha=0.05 one-sided) will also be displayed for descriptive purpose.

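### SAP 4.5 fits the primary model separately within each subgroup level and never estimates the difference between levels; with one uniform 6.6-point OI effect, exactly one of two equal levels would show p<0.05 about half the time (about 10% with no effect)

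*SAP*

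**What the plan says.** SAP 4.5 names three baseline factors: age class (below 65, 65 and over), gender and race/ethnicity. "Within each subgroup level, analyses (descriptive summaries and ANOVA models) will be performed on the primary endpoints", and this is done "according to the methods defined for the primary analysis in Section 7.1.1". In those models "the covariate related to the subgroup will not be considered". The main-analysis imputations are reused, and a level with no missing values is analysed without multiple imputation. At the blinded data review, small categories may be combined and unbalanced factors removed.

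SAP 4.5 itself mentions no p-value. It enters through 7.1.1.1 and 7.1.1.2, where the treatment difference is "displayed together with the corresponding two-sided 90% confidence interval" and "One-sided p-value (alpha=0.05 one-sided) will also be displayed for descriptive purpose".

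Protocol 9.5.3 makes subgroup analysis depend on adequate numbers and leaves the statistical detail to the SAP. No interaction term, interaction test or between-level contrast appears in SAP 4.5, SAP 7.1 or Protocol 9.5.3.

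**The concern.** A subgroup analysis asks whether the treatment effect differs between levels. Separate fits answer another question: what does each level show alone? With about 15 patients per arm per level, a uniform effect of useful size will often pass a nominal threshold in one level and miss it in the other. Read side by side, that looks like effect modification. In a proof-of-concept trial, such a reading could influence thinking about the population of a later study.

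Two rules make the side-by-side comparison less clean.
- SAP 7.1.1 drops the random site effect on non-convergence or a G-matrix that is not positive definite. Applied level by level, one level could keep the site effect while the other loses it.
- A level with missing data goes through multiple imputation and Rubin's rule; a level without does not.

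Randomization is stratified by site only (SAP 3.4.1.1), so the arms are not balanced by design within age, gender or race/ethnicity levels.

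**Working it through.** **Inputs**
- OI: "Assuming a standard deviation of 11.5 points for OI" (SAP 3.3).
- VFD: "Assuming a standard deviation of 8 days for VFD" (SAP 3.3).
- 60 evaluable patients, 1:1, so 30 per arm (SAP 3.3).
- Reference OI effect: "A difference between groups in 7-days OI of 6.6 points was significantly associated with 28-days mortality" (SAP 3.5.1). This is a proxy for clinical success, not an effect the design assumes. No reference effect is given for VFD.
- One-sided alpha 0.05, z = 1.645 (SAP 7.1.1).
- Assumption: one two-level factor split 50/50, so 15 per arm per level. The documents give no split.

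**The plan's own figure.** The plan states no subgroup error rate or power. Its nearest figure is a margin of error of at most 46.5% of the SD, or 5.35 OI points. With 30 per arm, 1.645 × √(2/30) = 0.425 SD, or 4.88 points, so the stated figure is not reproduced but is conservative. It is a separate matter and does not enter below.

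**Probability that exactly one level has p<0.05 under the same true effect in both**
- OI standard error per level: 11.5 × √(2/15) = 4.20.
- Power per level at common effect d: p = 1 − Φ(1.645 − d/4.20).
- Exactly one level below 0.05: 2p(1 − p).

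| Common OI effect (points) | p per level | Exactly one level p<0.05 |
|---|---|---|
| 0 | 0.050 | 0.095 |
| 2 | 0.121 | 0.213 |
| 3.3 | 0.195 | 0.314 |
| 6.6 | 0.471 | 0.498 |
| 10 | 0.769 | 0.355 |
| 13.2 | 0.933 | 0.125 |

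At 6.6 points the noncentral t gives 0.496, and splits from 60/40 to 80/20 give 0.51 to 0.57.

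For VFD the standard error per level is 8 × √(2/15) = 2.92 days. The same probability is 0.095 at 0 days, 0.28 at 2, 0.46 at 3.75 and 0.50 at 5 (assumed effects).

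**Role of the one-sided test.** With two-sided 0.05 at 6.6 points, p = 0.349 and 2 × 0.349 × 0.651 = 0.454. One-sidedness is not the main cause.

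**At least one nominal hit with no effect, per endpoint.** Levels of different factors contain the same patients. With balanced crossed binary factors, the estimates in an age level and a gender level correlate 0.5. Simulation gives 15.2% for two factors (four levels) and 19.3% for three (six levels).

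**After the fix**
- OI contrast between two equal levels: SE = √2 × 4.20 = 5.94; 90% half-width = 1.645 × 5.94 = 9.8 points.
- VFD contrast: SE = √2 × 2.92 = 4.13; half-width = 1.645 × 4.13 = 6.8 days.
- The contrast's false-signal rate stays at its nominal level whatever the common effect: 4.2% to 5.8% in simulation for a two-sided 5% test, and by construction 10% for a 90% interval excluding zero.
- Power for a true 6.6-point difference between levels is about 20% at two-sided 0.05.

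**The case against.** The strongest reply is that the plan attaches no decision to any subgroup. SAP 3.3 specifies no hypotheses and keeps p-values for description, and 4.5 prints a p-value only by cross-reference. The blinded review can merge or drop thin categories, and Protocol 9.5.3 asks for adequate numbers. A careful reader could subtract two level-specific differences and combine their standard errors, since levels of one factor hold different patients. The formal contrast has little power, and a pooled model may impose a common variance and common covariate effects.

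Much of this stands, and it limits the harm. It does not supply the missing estimate. Merging small categories does not stop level-by-level reading of those that remain. Hand subtraction ignores shared site effects and imputation. The pooling trade-off concerns how the model is specified; it is not a reason to leave out a contrast.

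Two stronger readings are tempting and are not supported.
- A reader might infer that chance differences mimic effect modification half the time in general. The table shows otherwise: 50% requires a common effect near 6.6 points and is close to the maximum for an even split.
- A reader might treat four to six levels as independent and compute 1 − 0.95⁴ = 18.5% to 1 − 0.95⁶ = 26.5% for a false hit under no effect. Overlapping patients make that too high; 15% to 19% is the supportable range, and it too assumes binary factors. SAP 5.4 lists five race/ethnicity categories, so the number of levels depends on the blinded review.

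**Conclusion.** The gap is real and modest: a cheap improvement to a descriptive analysis, not a flaw in the primary analysis. The plan shows level-specific effects with nominal p-values and never their difference.

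The 50% figure holds for one two-level factor, one endpoint, a 50/50 split, SD 11.5, 60 evaluable patients and a true OI effect of 6.6 points in both levels. It falls to about 31% at 3.3 points and about 10% with no effect. Baseline adjustment, the site effect, imputation and the percentile values assigned for death and extubation are not modelled, so the residual SD that matters is unknown. That a split result would steer a later trial is a risk of interpretation; nothing in the documents says it would.

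**What to change.** In SAP 4.5, replace the separate fits as follows. For each subgroup factor retained at the blinded review, fit one model on the full analysis population of the primary analysis, with the factor's main effect and a treatment-by-subgroup term, using the imputed datasets already planned. Age class and gender are already in the primary model; race/ethnicity would need its main effect added. Report the level-specific treatment differences and the between-level difference with its 90% interval. Do not display within-level p-values.

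The cost is a wording change and a small programming change. The contrast will be imprecise, with a half-width of about 9.8 OI points or 6.8 VFD days at a 50/50 split and more if the split is uneven. The SAP should therefore say that it is for estimation only.

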4.6 Covariates

The list of covariates to be used for analyses is described in section 7.1.1.

Standard/Forms/Template				
Title		Statistical Analysis Plan Template		
Code		Version	Effective Date	Page
PPD		01	29 Aug 2022	30 of 78

4.7 Pooling of sites

As described in section 3.4.1.1, Site is included in the statistical model as random effect, for the analysis of the primary efficacy endpoints (section 7.1.1.1).

Given the high number of sites and the relatively small number of patients per site, a pooling strategy will be considered as an option to be applied at the time of the Blinded Data Review Meeting.

4.8 Interim analyses

No interim analysis is foreseen.

4.9 Data Monitoring Committee

DMC meetings will be performed during the trial to monitor the safety of the patients and to protect study subjects from undue harm.

The following information will be analyzed for safety reason at each DMC meeting:

- Subject enrolment and disposition
- Protocol deviations
- Study discontinuations
- Demographics and baseline characteristics
- Medical history / conc meds
- Compliance to IMP
- Exposure to IMP
- Adverse events
- Clinical laboratory evaluation
- Vital signs
- ECGs

Further details will be provided in the DMC Charter, where all roles and responsibilities will be defined.

Access to unblinded information on the efficacy analyses is allowed on DMC request to balance patient safety risk against a possible gain in efficacy.

The DMC will consider the appropriateness of trial continuation if there is emerging evidence that reparixin is harmful.

After the 2nd DMC meeting (19Sept2024), the following analyses have been requested by the DMC members as additional analyses of the 2nd DMC meeting and in view of the 3rd DMC meeting:

- Descriptive statistics of Co-Primary endpoints. The purpose was not to monitor primary endpoints for early efficacy termination and no statistical test was to be performed.

Standard/Forms/Template				
Title		Statistical Analysis Plan Template		
Code		Version	Effective Date	Page
	PPD	01	29 Aug 2022	31 of 78

CCI [REDACTED]

- [REDACTED]
- [REDACTED]
 - [REDACTED]
 - [REDACTED]
 - [REDACTED]
 - [REDACTED]
- CCI [REDACTED]
- CCI [REDACTED]
- CCI [REDACTED]

- CCI [REDACTED]
- CCI [REDACTED]
 - [REDACTED]
 - [REDACTED]
 - [REDACTED]
- CCI [REDACTED]
 - [REDACTED]
- [REDACTED]
 - [REDACTED]
 - CCI [REDACTED]
- [REDACTED]

Standard/Forms/Template				
Title		Statistical Analysis Plan Template		
Code		Version	Effective Date	Page
PPD		01	29 Aug 2022	32 of 78

4.10 Handling of missing and incomplete data

All reasonable efforts will be made to reduce the rate of missing data. Investigators will be trained about the importance of patient retention and full data capture. Also, any reasonable attempts should be made by the investigators to emphasize continued subject's participation for the full duration of the trial.

Patients who discontinue the treatment will not be withdrawn from the study by default, but will be asked to complete safety and efficacy observations as per the protocol, unless otherwise they withdraw their consent. Patients who discontinue study treatment and decide to remain in the study by following the schedule of assessments and continuing to adhere to protocol requirements are defined as "retrieved dropout" patients (section 11.1.1 provides details on the definition).

For the main analyses of the primary endpoints, missing data will be managed as follows:

- Missing data due to death, preventing the collection of the endpoint, will be imputed with an unfavourable value (see section 4.4.1).
- Missing data in extubated patient, preventing the collection of the endpoint (for Change in OI at Day 7 only), will be imputed with a favourable value (see section 4.4.1).
- Missing data due to treatment discontinuation or any other reason (whichever the reason) will be handled by means of Multiple Imputation (MI) approach as detailed in Section 7.1.1.

Sensitivity analysis of the primary endpoints can be based on different missingness assumptions (section 7.1.2.1)

In the descriptive summaries, the number of subjects with missing data will be presented under the "Missing" category. Missing values will be included in the denominator count when computing percentages. When continuous data will be summarized, only the non-missing values will be evaluated for computing summary statistics. Any exception will be declared.

4.11 Changes in the planned analysis

The following changes have been included compared to the study protocol:

- Section 4.2.3: The Primary Analysis (including sensitivity analysis) is planned on the Randomized Set, as per Regulatory Authority request. Full Analysis set will be used for Supplementary Analysis and for analysis of secondary endpoints.
- Protocol section 9.5 mentions "Subjects who are free from events at the time of DB lock will be censored at the DB lock date. Reasons for discontinuation will be incorporated into the analysis for determining censoring and failure status. Specifically, study discontinuation for Adverse Event, Death, Lost to follow-up or other negative outcomes will be considered as failure events." As per SAP, other negative outcomes will not be considered in the analysis: only study discontinuation for Adverse Event, Death or Loss to follow-up will be considered as

Standard/Forms/Template				
Title		Statistical Analysis Plan Template		
Code		Version	Effective Date	Page
PPD		01	29 Aug 2022	33 of 78

failure events. Also, it has been added in the SAP that subjects free of events are censored at last available date.

- Protocol section 9.5.1.1 mentions “Normal distribution will be assessed graphically.”: for the two co-primary endpoints normality assumptions will be checked through visual inspection and statistical tests (Shapiro-Wilk’s test) as detailed in section 4.1, while for all other relevant endpoints normality is checked only via statistical test (Shapiro-Wilk’s test).
- **CCI**
[REDACTED]
- **CCI**
[REDACTED]
- Sensitivity and supplementary analysis have been added as described in SAP sections 7.1.2 and 0
- A new analysis has been added to be performed only on the subset of complete cases (i.e., without considering patients with missing endpoint) that reached Day 7 still intubated: details are provided in SAP section 7.1.3.6.
- The study protocol mentions among the secondary endpoints “Hospital-free days by day 28 and hospital discharge”: the endpoint will be evaluated only at day 28 (“Hospital-free days by day 28”) since at discharge the number of hospital-free days will be 0 by definition.

4.12 Data Review Meeting

BDRM will be held before DB lock. Any other details will be provided in the BDRM Plan or similar document. A BDRM report containing all decisions impacting the analysis will be prepared prior to DB Lock.

4.13 Software

All statistical analyses and data processing will be performed using Statistical Analysis Systems (SAS[®]) Software (release 9.4 or later).

5. Evaluation of Demographic and Baseline Characteristics

5.1 Subject enrolment and disposition

All presentations of subject disposition will be by treatment group, and overall.

For describing the subject disposition, the following populations will be summarized:

- Subjects screened overall (N).

Standard/Forms/Template				
Title		Statistical Analysis Plan Template		
Code		Version	Effective Date	Page
PPD		01	29 Aug 2022	34 of 78

- Subjects enrolled overall (N, 100%).
- Subjects enrolled but not randomized and reasons for non-allocation overall (N, %).
- Subjects randomized by treatment group, and overall (N, %).
- Number of subjects who completed each planned visit.
- Subjects randomized but not treated by treatment group, and overall (N, %).
- Subjects in each analysis set (RND, FAS, SAF, PP) and reasons for exclusion by treatment group, and overall (N, %). Reasons for exclusion from population are defined below:

Population	Reason for Exclusion
RND	Use reasons collected under “specify reason” in “Was the patient randomized=No” in “Randomization and IMP assignment” CRF form
FAS	Randomized but not treated
SAF	Randomized but not treated
PP	Randomized but not treated / protocol deviation leading to exclusion

With regards to percentage calculation:

- For the second and third bullet points the percentage denominator will be the number of ENR subjects,
- For the fourth bullet point, percentage overall denominator will be the number of ENR subjects, while percentage denominator within each treatment group will be the number of RND subjects;
- For the fifth and sixth bullet points, the percentage denominator will be the number of randomized subjects
- For the last bullet point, percentage will be based on RND set..

Listings will be provided based on ENR set.

5.2 Protocol violations

All the protocol deviations will be discussed case by case before unblinding of the treatment code, with the clinical team during the BDRM and described in the BDRM Report.

Number of occurrences and of subjects with at least one major, minor, and protocol deviation impacting on the analysis of primary endpoints that lead to exclusion from PP set will be summarized for each treatment and overall. Further details on PD management and classification are provided in the Protocol Deviation Management Plan and relevant documentation.

As an example, a non-exhaustive list of Protocol Deviations leading to exclusion from the PP set can be the following:

- Inclusion of the patient in the study in violation of inclusion/exclusion criteria
- Intake of prohibited medications

Standard/Forms/Template				
Title		Statistical Analysis Plan Template		
Code		Version	Effective Date	Page
PPD		01	29 Aug 2022	35 of 78

- Poor compliance with IMP
- Missing of assessments for the primary endpoint

Protocol deviations will be listed as well using the randomized set.

